4.2.6 Pharmacodynamic variables

4.2.6.1 Change in Eosinophils count

Peripheral blood eosinophils values and changes from baseline at each visit will be summarized using descriptive statistics for each treatment/weight group based on safety

analysis set. For DXD, only the PD samples collected within one dosing cycle after last dose will be included in the summary statistics during treatment period.

4.2.7 Body weight-adjusted clearance

Body weight-adjusted clearance will be calculated using the PK population model by AZ and will be summarized descriptively by treatment/weight group based on PK analysis set.

4.2.8 Immunogenicity Analysis

All listings and summary of ADA results will be based on safety analysis set. Immunogenicity of benralizumab (ADA) results by treatment/weight group will be listed by patient's study status with positive study status first then followed by patients with negative status, and schedule visit including ADA. All ADA positive samples will be tested for neutralizing antibodies (nAb) using a ligand binding assay. The nAb results will be reported as positive or negative.

The number and percentage of subjects who developed detectable ADA to benralizumab will be determined for each of the following categories. However, if the number of ADA positive subjects in the safety analysis set is small then the ADA variables may be listed only in the CSR.

- ADA positive at any time, including baseline and/or post-baseline. The denominator for percentage calculation is the number of subjects with any ADA result at baseline and/or post-baseline. This percentage is known as ADA prevalence.
- Treatment-emergent ADA positive, defined as either treatment-induced ADA positive (ADA negative at baseline and positive at post-baseline) or treatment-boosted ADA positive (baseline ADA titer that was boosted by greater than 4-fold following drug administration). The denominator for percentage calculation is the number of subjects with at least one post-baseline assessment. This percentage is known as ADA incidence.
- ADA positive at both baseline and at least one post-baseline measurement. The denominator for percentage calculation is the number of subjects with an ADA result at baseline and at least one post-baseline assessment.
- ADA positive at baseline only. The denominator for percentage calculation is the number of subjects with an ADA result at baseline.
- Persistently positive ADA, defined as having at least 2 post-baseline ADA positive measurements with at least 16 weeks (112 days) between the first and last positive measurements, or an ADA positive result at the last available assessment. The

denominator for percentage calculation is the number of subjects with at least one post-baseline assessment.

- Transiently positive ADA, defined as having at least one post-baseline ADA positive measurement and not fulfilling the conditions for persistently positive. The denominator for percentage calculation is the number of subjects with at least one post-baseline assessment.
- nAb positive at baseline and/or post-baseline (nAb prevalence). The denominator for percentage calculation is the number of subjects with any ADA result at baseline and/or post-baseline.
- Treatment-induced nAb positive (nAb incidence); defined as nAb negative at baseline (or ADA negative at baseline) and nAb positive at any post-baseline visit. Subjects who are ADA-negative at baseline are included to ensure that all subjects who are nAb positive for the first time post-baseline satisfy this definition, given that all subjects who are ADA negative at baseline do not have a nAb result reported.

For ADA summaries at a single time point (e.g. baseline ADA or by visit) the corresponding titre summary will be based on the titre of the positive sample for that particular visit. For proportions summarising across visits (e.g. any ADA post-baseline) the corresponding titre summaries will be based on the maximum titre of all positive samples for each subject.

The hypersensitivity AEs reported on treatment period will be presented by preferred term for ADA status.

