7.1.1 Procedures for discontinuation of study treatment

A patient that decides to discontinue study treatment will always be asked about the reason(s) and the presence of any AEs. The date of last administration of study treatment should be documented in the eCRF. Patients permanently discontinuing study treatment should be given locally available standard of care therapy, at the discretion of the investigator.

All patients who prematurely discontinue IP should return to the study site and complete the procedures described for the Early Discontinuation (DXD) Visit within 4 weeks after the last dose of IP. At that visit, although no longer on IP, patients should be encouraged to remain in the study. Although only AEs, SAEs, and concomitant medication are required to be collected after the DXD Visit, safety data collection should continue according to the study protocol.

Note that in this case, the DXD Visit replaces the nearest regular visit while the following visits continue as possible. If the patient or guardian does not agree to continue in-person study visit(s), a modified follow-up, such as telephone contact with the patient or guardian, should be arranged to ensure the collection of safety information through the 48-week time point.

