8.3.2 Time period and frequency for collecting AE and SAE information

Adverse events and SAEs will be collected from the time of signature of the ICF throughout the treatment period and including the follow-up period (Visit 14).

All SAEs will be recorded in the eCRF and reported to the sponsor or designee within 24 hours, as indicated in [Appendix C](#). The investigator will submit any updated SAE data to the sponsor within 24 hours of it being available.

Investigators are not obligated to actively seek AE or SAE in former study patients. However, if the investigator learns of any SAE, including a death, at any time after a patient's last visit and he/she considers the event to be reasonably related to the study treatment or study participation, the investigator may notify the sponsor.

The method of recording, evaluating, and assessing causality of AE and SAE and the procedures for completing and transmitting SAE reports are provided in [Appendix C](#).

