9.5.4.2 Immunogenicity

Anti-drug antibodies (ADA) to benralizumab will be summarised using descriptive statistics at each visit by treatment/weight group. Anti-drug antibody titres-time profiles of benralizumab by treatment/weight group will be generated. The impact of ADA on PK and eosinophil level will be assessed. The potential association of ADA with safety will be evaluated. Any hypersensitivity AEs reported during the on-study period will be evaluated by ADA status.

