3.1.3 Study Periods

The following study periods are defined for analysis purposes:

- Pre-Treatment (Screening period): starting on the date of the first study procedure and ending one day prior to date assigned study treatment (for subjects assigned study treatment) or on the date of the last study procedure (for screening failures). If any subject is re-screened, the latest available screening will be used for this purpose.
- On-treatment period: defined as starting between day of first dose of study treatment and scheduled end of treatment (EOT) visit or early discontinuation (DXD) visit for those patients who prematurely discontinue study treatment, inclusive. If both EOT and DXD visits are missing then the upper limit of the on-treatment period is defined as the day of last dose of study treatment + 56 days. If the upper limit is after the end of on-study period, then the upper limit is end of on-study period
- On-study period: starting on the date of first dose of IP and ending on the study completion or withdrawal date

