4.2.13 Laboratory variables

All continuous laboratory parameters will be summarized descriptively by absolute value by each planned visit by treatment/weight group, together with the corresponding changes from baseline using the safety analysis set. These summaries will be produced for the on-study period, as defined in section 3.1.3. The summary statistics presented will be the minimum, 1st quartile, median, 3rd quartile, maximum, mean and SD. Mean changes from baseline over time will also be plotted by treatment group. All variables will be summarized in SI units, with the exception of blood eosinophil counts which will be summarized in both SI and conventional units.

Central laboratory normal reference ranges will be used for the identification of abnormalities. A shift table will be produced for each laboratory variable to display low, normal, high and missing values. The shift tables will present baseline and maximum/minimum/last post-baseline values for each variable.

Shift plots showing each individual patients' laboratory value at baseline and at maximum/minimum/last value post-baseline will be produced for each continuous laboratory variable. If any laboratory variables show any unusual features (high or low values or a general shift in the data points) at other time points then shift plots of these data may be produced. The diagonal line of no change, and horizontal and vertical reference lines indicating the limits of the normal reference ranges, will also be displayed on the shift plots.

Maximum post-baseline TBL elevations by maximum post-baseline ALT and AST will be presented, expressed as multiples of ULN. TBL will be presented in multiples of the following ULN ≤ 1.5 , >1.5 -2, >2 , and AST and ALT will be presented in multiples of the following ULN ≤ 1 , >1 -3, >3 -5, >5 -10, >10 .

Maximum post-baseline TBL will be presented (<2 and ≥ 2 x ULN) against maximum post-baseline ALT (<3 , ≥ 3 - <5 , ≥ 5 - <10 , and ≥ 10 x ULN), expressed as multiples of ULN. This will be repeated to show maximum post-baseline TBL against maximum post-baseline AST. Data for patients with ALT or AST ≥ 3 x ULN, and bilirubin ≥ 2 x ULN will be presented, which will include all visits for this subset of patients.

For urinalysis data, a shift table will be generated to present changes from baseline to maximum post-baseline value for each variable and will include subjects with both baseline and post-baseline data.

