4.2.14 Vital signs

All vital signs variables including height, weight and BMI will be summarized by absolute value at each visit by treatment/weight group using the safety analysis set, together with the corresponding changes from baseline. These summaries will be produced for the on-treatment period, as defined in section 3.1.3. The summary statistics presented will be the minimum, 1st quartile, median, 3rd quartile, maximum, mean and SD. The normal reference ranges listed in Table 2 and Table 3 will be used for the identification of individual abnormalities. A shift table will be produced for each vital sign variable to display low, normal, high and missing values. The shift tables will present baseline and maximum/minimum/last post-baseline values for each variable.

Shift plots showing each individual patient's vital signs value at baseline and at maximum/minimum/last value post-baseline will be produced for each continuous vital sign variable.

All recorded vital signs data will be listed.

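### SAP 4.2.8 limits the hypersensitivity-by-ADA table to the treatment period, while the protocol specifies the on-study period and the SAP declares no change

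*SAP*

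**What the plan says.** **Hypersensitivity by ADA status.** Protocol 9.5.4.2: "Any hypersensitivity AEs reported during the on-study period will be evaluated by ADA status". SAP 4.2.8: "The hypersensitivity AEs reported on treatment period will be presented by preferred term for ADA status".

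**What the periods mean.** SAP 3.1.3 defines two periods, both starting at first dose. The on-treatment period ends at the "scheduled end of treatment (EOT) visit or early discontinuation (DXD) visit for those patients who prematurely discontinue study treatment, inclusive". If both visits are missing, it ends 56 days after the last dose, but not later than the end of the on-study period. The on-study period runs to study completion or withdrawal.

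**Other adverse event summaries.** SAP 3.3.6.1 and 4.2.12.1 classify adverse events by onset in the on-study period.

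**Declared changes.** SAP Section 1 says departures from the protocol will be described in Section 6. Section 6 reports none.

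**Vital signs.** SAP 4.2.14: "These summaries will be produced for the on-treatment period, as defined in section 3.1.3". The laboratory section, SAP 4.2.13, differs: "These summaries will be produced for the on-study period, as defined in section 3.1.3". SAP Table 1 gives vital signs a Week 52 window (Day 349 onwards), and SAP 4.1 says the analyses take in the Week 52 follow-up visit. Protocol 9.5.5 names no period for vital signs.

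**End of safety follow-up.** For families who decline in-person visits after stopping treatment, protocol 7.1.1 arranges modified contact "to ensure the collection of safety information through the 48-week time point". Protocol 8.3.2 collects adverse events through Visit 14, which is Week 52.

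**The concern.** The SAP replaces the protocol's analysis period with a shorter one and does not say so. The hypersensitivity-by-ADA table would then be the only adverse event summary on the shorter period. If a late event occurred, its count would not agree with the main adverse event tables, and nothing in the SAP would explain the difference.

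The time lost falls unevenly. A completer is counted for 56 days after the last dose (Day 280 to Day 336), and so is a child with neither EOT nor DXD. A child who attends DXD on time is counted for at most 28 days after the last dose, although protocol 7.1.1 still requires adverse events to be collected after that visit.

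The table matters because protocol 2.3 names hypersensitivity reactions, with anaphylaxis and immune complex disease as examples, as a theoretical risk of ADA. The same paragraph adds that ADA development has not been associated with an increase in adverse events, so few events should be expected.

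**Working it through.** The plan states no figure to reproduce. The check compares the period definitions and subtracts scheduled days.

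**Inputs**
- Last scheduled dose Day 280, EOT Day 336, follow-up (Visit 14) Day 362; windows of ±7 days at EOT and follow-up (protocol Table 1).
- DXD within 4 weeks, that is 28 days, of the last dose (protocol 7.1.1).
- Period definitions from SAP 3.1.3.

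**Completers.** Time on study but outside the on-treatment period = 362 − 336 = 26 days, or 26/362 = 7% of Days 0 to 362. With the visit windows, the range is (362 − 7) − (336 + 7) = 12 days to (362 + 7) − (336 − 7) = 40 days.

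**Early discontinuers.** With last dose on Day D, DXD at the 28-day limit and follow-up to Day F, the time outside is F − (D + 28). A DXD before the limit makes it longer, and a late DXD shortens it day for day.

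| Last dose (Day) | DXD by (Day) | Outside, F = 362 | Outside, F = 336 |
|---|---|---|---|
| 0 | 28 | 334 | 308 |
| 28 | 56 | 306 | 280 |
| 56 | 84 | 278 | 252 |
| 112 | 140 | 222 | 196 |
| 168 | 196 | 166 | 140 |
| 224 | 252 | 110 | 84 |
| 280 | 308 | 54 | 28 |

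So 54 days is the minimum for a timely DXD with follow-up to Day 362. Day 280 is the last planned dose; a child who stops and misses a planned dose had the last one on Day 224 or earlier, which gives at least 110 days. The right-hand column applies if contact ends at 48 weeks, as protocol 7.1.1 allows for modified follow-up. The two columns differ by 362 − 336 = 26 days.

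**Missing both EOT and DXD.** With last dose on Day 280, the fallback gives 280 + 56 = Day 336, the same as a completer.

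**Vital signs.** Protocol Table 1 schedules vital signs at Visit 14, Day 362. That lies after EOT and therefore outside the on-treatment period, so the measurement has a window in SAP Table 1 but no place in the summary. Protocol 7.1.1 does not require vital signs after DXD, so moving to the on-study period adds essentially one visit row.

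**The case against.** The strongest defence is that ending the table at EOT or DXD matches ADA sampling. Protocol Table 7 places the last ADA sample at Visit 13 or DXD, with no blood drawn at Visit 14, so a later reaction can only be classified from an earlier result. That is correct, but it does not justify the SAP text. SAP 4.2.8 already defines subject-level ADA categories (any positive, treatment-emergent, persistent, transient), and these can classify a later event. If the shorter period was intended, Section 6 should say so.

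It can also be said that SAP 4.2.8 omits the hyphen and does not refer to 3.1.3, so the wording may only be loose. The defined on-treatment period remains the natural reading, and on any reading it is not the protocol's term.

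A reader might infer more than the documents support:
- **That late reactions are lost.** They are not. They stay in the on-study adverse event summaries and the listings, and SAP 4.2.14 lists all recorded vital signs.
- **That a reaction which causes a child to stop is dropped.** It precedes DXD, and the on-treatment period includes DXD, so it is counted. Only new events after DXD are missed.
- **That the protocol also sets the on-study period for vital signs.** It names no period. That inconsistency is internal to the SAP and is not a change that Section 6 had to declare.
- **That the laboratory section shows follow-up data being kept.** No laboratory samples are scheduled at Visit 14, so the comparison shows inconsistent wording and little more.
- **That the Week 52 vital-sign window can never be filled.** Windows use actual dates, so an EOT visit at least 349 − 336 = 13 days late would fall in it. It is simply not filled by Visit 14 data.
- **That one event shifts the table by about 3 percentage points (1 in 30).** The table is split by ADA status, and the sizes of those groups are unknown.

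**Conclusion.** The point holds for the hypersensitivity-by-ADA table: protocol and SAP name different periods, and the change is undeclared. Followed as written, the table omits new events over 26 nominal days for completers. For early discontinuers it omits at least 54 days, given DXD within 28 days of the last dose and adverse event follow-up to Day 362. The effect is confined to one cross-tabulation and is likely to involve few events or none. This is a minor point about agreement between documents and between tables.

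The vital-sign point is secondary and affects one visit row. The difference between protocol 7.1.1 and 8.3.2 is a separate question of data collection, not an SAP analysis choice. The 48-week wording covers only the modified contact, and 7.1.1 also says safety collection should continue according to the protocol. It does, however, determine whether the 54 days or the 28 days in the last row of the table applies to a child on modified follow-up.

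**What to change.** 1. In SAP 4.2.8, name the on-study period of SAP 3.1.3 for the hypersensitivity-by-ADA table, as in protocol 9.5.4.2, and state that later events are classified by the subject-level ADA category. If the shorter period is intended, declare and justify it in Section 6.
2. In SAP 4.2.14, use the on-study period so that Visit 14 vital signs are summarised as well as listed, in line with SAP Table 1 and SAP 4.1.
3. Reconcile the 48-week end of modified follow-up in protocol 7.1.1 with adverse event collection through Visit 14 in 8.3.2.

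The first two are wording changes in the SAP and need no new assessments, since the data are already scheduled for collection. The third is a protocol clarification.

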4.2.9 Forced expiratory volume in first second (FEV1)

FEV₁ measurements and changes from baseline at each visit will be summarized using descriptive statistics for each treatment/weight group based on safety analysis set.

4.2.10 Asthma control questionnaire (ACQ-IA)

The mean ACQ-IA score and change from baseline at each visit will be summarized for each time point using descriptive statistics for each treatment/weight group based on safety analysis set.

The number and percentage of ACQ-IA responders (yes, no), ACQ-IA responses (improved, no change, deterioration), subject's asthma control (well controlled, partially controlled, and not well controlled) at each post-baseline visit will be also be presented.

4.2.11 Global impression of change

The CGIC and PGIC-IA responses will be summarised by treatment/weight group and visit using the safety analysis set. The number and percentage of patients will be presented for CGIC, PGIC-IA, and for the response agreement between CGIC and PGIC-IA.

The number and percentage of patients defined as responders based on categorized responses for CGIC and PGIC-IA (improved, much improved, very much improved) will also be presented by treatment/weight group and visit.

4.2.12 Safety Analysis

All safety and tolerability variables will be summarised by treatment/weight group and overall and evaluated descriptively using the safety analysis set. No formal hypothesis testing of safety data is planned.

Out-of-range values for safety laboratory, vital signs, and ECGs will be flagged in individual listings.

4.2.12.1 Adverse Events

All AEs experienced by the patients will be collected throughout the study, as per CSP Table 1, and will be coded by the AstraZeneca designee using the latest version of MedDRA.

The timings of AEs will be assigned to the period in which they occurred. AEs occurring during the screening period will be listed, but not summarised separately.

AEs or Serious Adverse Events (SAEs) will be categorised as occurring on-study period based on their onset date:

An overall summary table will be produced showing the number and percentage of patients with at least one AE in each of the following categories: any AEs, SAEs, AEs with outcome of death, and AEs leading to discontinuation of IP (DAEs). The total number of AEs in the different AE categories in terms of AE counts will also be presented (i.e. accounting for multiple occurrences of the same event in a patient).

AEs, SAEs, AEs with outcome of death, and DAEs will be summarised by SOC and PT assigned to the event using the MedDRA dictionary by descending frequency order in the overall benralizumab treatment group. For each PT, the number and percentage of patients reporting at least one occurrence of the event will be presented (i.e. subjects with multiple occurrences of the same PT will only be counted once). A summary of the most common (frequency of $>5\%$) AEs in any treatment group will be presented by PT.

AEs and SAEs will be summarized by PT and Investigator's causality assessment (related versus not related) and maximum intensity. If a patient reports multiple occurrences of the same AE within the same reported period, the maximum intensity will be taken as the highest recorded maximum intensity (the order being mild, moderate, and severe).

Separate listings of subjects with AEs, SAEs, AEs with outcome of death, or DAEs will be presented.

4.2.13 Laboratory variables

All continuous laboratory parameters will be summarized descriptively by absolute value by each planned visit by treatment/weight group, together with the corresponding changes from baseline using the safety analysis set. These summaries will be produced for the on-study period, as defined in section 3.1.3. The summary statistics presented will be the minimum, 1st quartile, median, 3rd quartile, maximum, mean and SD. Mean changes from baseline over time will also be plotted by treatment group. All variables will be summarized in SI units, with the exception of blood eosinophil counts which will be summarized in both SI and conventional units.

Central laboratory normal reference ranges will be used for the identification of abnormalities. A shift table will be produced for each laboratory variable to display low, normal, high and missing values. The shift tables will present baseline and maximum/minimum/last post-baseline values for each variable.

Shift plots showing each individual patients' laboratory value at baseline and at maximum/minimum/last value post-baseline will be produced for each continuous laboratory variable. If any laboratory variables show any unusual features (high or low values or a general shift in the data points) at other time points then shift plots of these data may be produced. The diagonal line of no change, and horizontal and vertical reference lines indicating the limits of the normal reference ranges, will also be displayed on the shift plots.

Maximum post-baseline TBL elevations by maximum post-baseline ALT and AST will be presented, expressed as multiples of ULN. TBL will be presented in multiples of the following ULN ≤ 1.5 , >1.5 -2, >2 , and AST and ALT will be presented in multiples of the following ULN ≤ 1 , >1 -3, >3 -5, >5 -10, >10 .

Maximum post-baseline TBL will be presented (<2 and ≥ 2 x ULN) against maximum post-baseline ALT (<3 , ≥ 3 - <5 , ≥ 5 - <10 , and ≥ 10 x ULN), expressed as multiples of ULN. This will be repeated to show maximum post-baseline TBL against maximum post-baseline AST. Data for patients with ALT or AST ≥ 3 x ULN, and bilirubin ≥ 2 x ULN will be presented, which will include all visits for this subset of patients.

For urinalysis data, a shift table will be generated to present changes from baseline to maximum post-baseline value for each variable and will include subjects with both baseline and post-baseline data.

shift table will also be provided for each urinalysis qualitative assessment using the number and percentage of patients with baseline results of negative, trace or positive versus the maximum on treatment result of negative, trace or positive.

The number of patients with treatment-emergent changes will also be summarised.

Any data outside the laboratory reference ranges will be flagged and explicitly noted on the listings that are produced.

